The list of the schools accepting to participate in the RCT has to be sent to OED Institute in **Spring/early Summer 2010, as soon as the agreement with the schools will be taken**. The results of the random allocation will be communicated to the centers approximately **two weeks after**.

After the random allocation, the training of teachers in the schools allocated to the intervention groups will be organized and managed by the local project team.

In all the schools, independently from their group of allocation, **3/4 classes** in the target grade will be administered the questionnaire a first time in **October/November 2010** for the pre-test survey and a second time in **May 2011** for the post-test survey, and where possible a third time in **May 2012** for one year follow-up survey.

The 4 classes will be chosen by the local project team in agreement with the school. The list of the chosen classes will be sent to the OED team. Each class will be attributed an **unique code** by the OED team, to be put on the **first page of the questionnaire**. This code, together with the school code, is needed to take into account the school/class level at the analysis stage.

6. Questionnaire

The questionnaire to be administered at the baseline, post-test and follow-up surveys is derived from that used in the EU-Dap study. The **modified questionnaire** contains some new questions on social status of the family, more details on the use of alcohol, and some new validated questions on intermediate variables.

[figure not shown]
The main sections of the questionnaire are:

- social environment;
- own tobacco, alcohol and substance use;
- knowledge & opinions about substances
- substance use in the nearest environment;
- family and social environment;
- school environment and school climate;
- problems and skills.

With the aim to include already validated questions in the questionnaire, most of the questions have been caught from the EDDRA data bank, but some have been taken from other surveys. The sources of the modified questionnaire are listed here.

Question # Sources

<pre>(4) (5,6) (7-8-9-10) (11) (12) (13) (14) (15) (16, 17) (18) (19, 20) (21, 22, 23) (24) (25) (26, 27) (28) (29) (30) (31) (32) (33, 34) (35)</pre>	RATING (Swedish cohort) ESPAD 2003
(37)	HBSC 94, 98
(38)	ESPAD 2003

(39)	EMCDDA
(40)	RATING (Swedish cohort)
(41)	EMCCDDA + ESPAD 2007

(42) Fit 5-6 Stell dir vor. (Germany)

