The questionnaire will be translated and sent by OED staff to the evaluators of the participating countries. After reaching a general agreement on the acceptability of the questions, the questionnaire will be piloted in a class (see below).

In the translation of the questionnaire, special care is needed for **question 20**, where the translation/adaptation team must choose the list of substances to be included in the examples. It is in fact possible to change the list of the drugs according to the local conditions.

On the contrary, it is necessary that **all other questions closely match the standard questionnaire**. In case it is needed to delete questions, an agreement has to be reached with OED staff.

7. Questionnaire's Pilot Study

A small **piloting** of the questionnaire should be performed at least at the level of one of the participating countries, but if possible in all the countries.

The aims of the Pilot Study are:

[figure not shown]
- 1. to test the anonymous code completion
- 2. to test the understandability of the questions
- 3. to test the general acceptance of the questions

The pilot study of the questionnaire will take place administrating the questionnaire to **a class** of the chosen the target grade. **Together with the questionnaire** to be filled, **a short form** assessing the understandability of the questionnaire will be administered to the pupils. The **problems** encountered by the pupils in filling the questionnaire and the anonymous code will be taken into account to improve the Arabic version of the questionnaire.

Instructions for the pilot study will be provided together with the short questionnaire. Results, problems encountered by the pupils and solutions adopted will be shared with OED staff and, if needed, a **final version of the questionnaire** will be elaborated by June 2010 at the latest. From this version, the centers will print the copies for the randomized evaluation study.

The questionnaire can be simple or colorful, according to the possibilities of the center.

It will be needed to provide OED with a complete **back-translation of the questionnaire** (from Arabic to English). The back-translation will be sent to OED staff, who will check the translation and will give suggestions when needed. The back-translation should be provided by the end of May 2010 at the latest. From the back-translated version a mask for the data entry will be prepared.

8. Baseline (pre-test) survey

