A **pre-test survey** will be undertaken to measure the prevalence of substance use at baseline, and to measure the main confounding factors. It will be also essential to evaluate the effectiveness of the program in preventing the initiation of tobacco, alcohol and drugs use, taking into account the baseline status of the pupils as regards substance use.

The pre-test survey will be administered in **October/November 2010**. The questionnaire will be distributed to the pupils by the center staff and will be self-completed. The same questionnaire will be administered in the subsequent surveys. Before administering the questionnaire to the pupils it is needed to fill the **school** and **class code** (as provided by OED) on the first page. This code is very important to take into account school and class level at the analysis stage.

The administration of the questionnaires will be managed in the classes by **the project manager and his/her assistants**, in agreement with the schools. During the administration of the survey, **the teachers can leave the class**. As regards the presence or absence of the teacher during the surveys, individual agreement will be taken for each class inside the country.

For pupils **absent in the class the very day of the survey**, the teacher will be provided with an empty questionnaire and a pre-paid envelope and will be asked to contact the pupil to obtain the questionnaire filled. The questionnaire will be then sent to the center by the pupil him/herself.

9. Data collection and input of baseline survey

The OED Institute will provide the partners with an **internet mask**, which will be available on the www.eudap.net website. The countries will perform the data entry locally on the internet mask. OED staff will manage the **data management**, performing all the checking needed to provide the final database for the analysis. All these tasks will be performed by [name] [name].

[figure not shown]

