For a correct data input of the questionnaires, it will be needed to provide a translation of the individual anonymous code near the code filled by the pupil in the first page of the questionnaire. A **"translation book"** will be agreed during the pilot phase (spring 2010). It is important that the codes will be translated from Arabic to Roman characters in the same way for all the surveys. In fact, in case characters will be translated in a different way in the various survey, the second code won't match with the first one and questionnaires will be excluded from the effectiveness analysis.

The **analysis** of the baseline survey will be performed by the OED Institute which will provide the partners with **pooled descriptive statistics** and **specific statistics by country**, approximately 4-6 months after the survey.

10. Process evaluation

For the evaluation of the process, a specific protocol ("**process monitoring protocol**") is provided, including details on the forms to be used and the procedures to follow.

For the process evaluation some tools are provided:

- 1. a form regarding the activities implemented in the class, to be completed by the teacher at the end of each unit, for a total of 12 forms;
- 2. a form regarding the implementation of other prevention activities (other than Unplugged) in the intervention schools;
- 3. a form regarding the prevention activities implemented in the control schools;
- 4. a form on the activities of the parents workshops, to be completed by the Unplugged trainer at the end of each seminar, for a total of 3 forms;
- 5. a form investigating the overall satisfaction of the teachers with the program;
- 6. a form investigating the overall satisfaction of the pupils with the program.

The forms should be provided to the teachers during the Unplugged training. The **program manager will keep contacts** with the teachers once a month to monitor the implementation of the Unplugged units and give support. At the end of the program, he/she will collect the process forms (both teachers' and pupils' forms). He/she will also responsible to **enter** the process questionnaires data in a specific mask provided by the OED Institute. The OED Institute will analyse these data and will provide the partners feedback on the implementation of the units and on the possible improvements suggested by the teachers.

11. Follow-up (post-test) survey

The post-test survey will be administered in **May 2011**.

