The **same questionnaire** administered in the baseline survey will be used, following the same procedures, according to the protocol.

Again, it will be needed to fill the **school** and **class** code on the first page of the questionnaires before the administration. Following the same procedures adopted for the pre-test survey, the administration of the questionnaires will be managed in the classes by the **project manager** and his/her assistants, and the **teachers** will decide if remain or leave the class.

[figure not shown]
Again, for pupils **absent in the class the very day of the survey**, the teacher will be provided with an empty questionnaire and a pre-paid envelope and will be asked to contact the pupil to obtain the questionnaire filled. The questionnaire will be then sent to the center by the pupil him/herself.

The self-generated anonymous code will be used to **link pre-test with post-test** questionnaires while protecting the personal identification. This system has the purpose to prevent the linkage between personal identifiers allowing at the same time the linkage between the different questionnaires filled in by the same subject.

12. Data collection and input of post-test survey

As for the baseline survey, the post-test questionnaires will be entered locally in the **internet mask** provided by OED. Afterwards, OED staff will perform all the checking needed to provide the final database to be used for the analysis.

Again, it will be needed to put a translation of the individual anonymous code near the code filled by the pupil in the first page of the questionnaire.

The analysis of the post-test survey will be performed by the OED Institute which will provide the partners with **effectiveness results pooled and by country**, approximately 4-6 months after the post-test survey.

13. 1-year follow-up survey

It is possible that a further survey will be funded and will take place 1 year after the end of the program, in **May 2011**.

In this case, the **same questionnaire** administered in the baseline and post-test survey will be used, following the same procedures, according to the protocol.

As usual, the questionnaires will be entered in the internet mask, the OED Institute will manage the data input, data management, and data analysis, and will provide the partners with **effectiveness results pooled and by country**, approximately 4-6 months after the survey.

14. Publication of data

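### Section 9 drops questionnaires whose transliterated codes do not match, though unmatched post-test outcomes can still be assigned to school and arm: a sure loss of precision and an avoidable, unquantified risk of bias

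*Protocol*

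**What the plan says.** Pupils identify themselves by a self-generated anonymous code, which links the surveys (Protocol section 11). At baseline, section 9 states that "it will be needed to provide a translation of the individual anonymous code near the code filled by the pupil"; section 12 repeats the step at post-test: "Again, it will be needed to put a translation of the individual anonymous code near the code filled by the pupil". If the two renderings differ, section 9 says that "the second code won't match with the first one and questionnaires will be excluded from the effectiveness analysis".

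Three safeguards are described:

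- Section 9 provides for a transliteration key, agreed in the pilot phase: "It is important that the codes will be translated from Arabic to Roman characters in the same way for all the surveys".
- Section 7 lists among the aims of the pilot "to test the anonymous code completion". The pilot is one class, required in at least one country and wished for in all.
- Sections 9 and 12 have OED staff check the data before the final database is made.

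On data handling, section 9 says "The countries will perform the data entry locally on the internet mask". On allocation, section 5 says "The results of the random allocation will be communicated to the centers approximately" two weeks after the school lists are sent, so the centres know the arms before any survey. Sections 8 and 11 require the school and class codes to be filled in on the first page before each administration.

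**The concern.** The exclusion in section 9 is worded for the effectiveness analysis as a whole, not for the part of it that needs linked records. Schools are the randomised unit and the school code is on the form. A post-test questionnaire without a baseline partner can therefore still be placed in its arm and cluster, and its outcome can be counted in a comparison of post-test prevalence.

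Two things are at stake. The first is precision, which is lost whenever codes fail to match. The second is the comparison itself. Inclusion would depend on something that happens after randomisation, namely a code that is both written and transliterated the same way twice. If that were related to substance use, and differently so in the two arms, the linked comparison would be distorted.

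**Working it through.** **Planned numbers.** Table 1 reproduces as schools × 4 classes × pupils per class:

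- Unplugged: 480 + 840 + 600 + 700 + 500 + 700 = 3820 (36 schools)
- Usual Curriculum: 480 + 960 + 600 + 800 + 500 + 800 = 4140 (39 schools)
- Total: 7960 (75 schools)

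**Precision.** The protocol gives no match rate and no intracluster correlation (ICC), so both are assumed. With a fraction u unmatched, the linked sample is 7960 × (1 − u). The mean school size is 7960 / 75 = 106.1 pupils. With m pupils per school, the effective information per school is m / [1 + (m − 1) × ICC]. For u = 0.20, m falls to 84.9:

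- ICC 0.01: 106.1 / 2.051 = 51.7 falls to 84.9 / 1.839 = 46.2, a loss of 11%
- ICC 0.05: 106.1 / 6.257 = 17.0 falls to 84.9 / 5.196 = 16.3, a loss of 4%

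| Unmatched (assumed) | Linked pupils | Information lost, ICC 0.01 | Information lost, ICC 0.05 |
|---|---|---|---|
| 10% | 7164 | 5% | 2% |
| 20% | 6368 | 11% | 4% |
| 30% | 5572 | 17% | 6% |

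This takes schools as equal in size and mismatches as scattered over all 75.

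**Bias.** Let l1 and l0 be the exclusion rates among users and non-users in an arm with true prevalence p. The prevalence seen among linked pupils is p(1 − l1) / [p(1 − l1) + (1 − p)(1 − l0)]. The observed odds ratio is then the true one multiplied by [(1 − l1)/(1 − l0)] in the intervention arm, divided by the same quantity in the control arm. It is unchanged unless that quantity differs between arms. With p = 10% in both arms, no true effect, and all exclusion rates assumed:

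| Exclusion | Observed prevalence, intervention vs control | Odds ratio |
|---|---|---|
| 20% everywhere | 10.0% vs 10.0% | 1.00 |
| 25% vs 15% by arm, unrelated to use | 10.0% vs 10.0% | 1.00 |
| 30% of users, 20% of non-users, both arms | 8.9% vs 8.9% | 1.00 |
| 30% of intervention users, 20% of all others | 8.9% vs 10.0% | 0.875 |
| 40% of intervention users, 20% of all others | 7.7% vs 10.0% | 0.75 |

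For the fourth row: 0.10 × 0.70 = 0.07, 0.90 × 0.80 = 0.72, 0.07 / 0.79 = 8.9%; odds ratio 0.70 / 0.80 = 0.875.

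The third pattern leaves the odds ratio alone but shrinks a risk difference. A true 7% vs 10% becomes 6.2% vs 8.9%, that is 2.7 points instead of 3.0, with the odds ratio still 0.68.

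In the last two rows total exclusion is 21% or 22% against 20%, so match rates by arm alone would not show the problem.

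**What the safeguards reach.** The key and the OED checks address inconsistent rendering by staff. They do not correct a pupil who writes a different code in May from the one in October or November. The pilot, as described, has one administration. It can show whether pupils can complete the code, not whether they repeat it.

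**The case against.** The sentence in section 9 can be read as a warning to centres to transliterate consistently, more than as a definition of the analysis population, and it comes straight after the safeguard. Section 8 also aims at preventing initiation, given each pupil's baseline status. An unlinked post-test record cannot show initiation, so leaving it out of a linked analysis follows from an anonymous cohort design. Matching tolerance and sensitivity analyses are often left to a SAP, which is not at hand.

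Most of this stands. The linked analysis should stay, and the absence of a matching algorithm is not held against the protocol. What remains is the written consequence: it covers the effectiveness analysis without limit, although part of that analysis needs no link.

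Stronger readings are tempting but not supported:

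- A reader might infer that one differing letter removes a pupil. The protocol gives no matching rule, so this is not established.
- A reader might infer that allocation-aware centre staff do the transliteration. Only data entry is stated to be local; who writes the Roman version is not said.
- A reader might infer that the analysed sample falls short of a promised 7960. That figure is the approximate number surveyed, and the inputs to the sample size are not shown, so an allowance for linkage loss can be neither confirmed nor excluded.
- A reader might infer that the rule biases the trial. Purely clerical mismatch unrelated to use costs precision only, and the protocol offers no evidence of a mismatch that depends on both use and arm.

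**Conclusion.** The point holds as a modest one. Any mismatch that occurs costs precision: at an assumed 20% unmatched, 1592 of 7960 pupils leave the linked sample, and about 4 to 11% of the information goes at an assumed ICC of 0.05 to 0.01. The loss would differ if mismatches gathered in particular schools or countries.

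Distortion of the odds ratio is a possibility whose size and direction the protocol does not allow anyone to state. The values 0.875 and 0.75 illustrate assumed rates and estimate nothing about this trial. This is a cheap improvement worth making, not a defect that invalidates the design.

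**What to change.** 1. Enter the code in its original Arabic characters in the internet mask, and transliterate once, by program, at OED. This should be in place before baseline data entry (January/February 2011 in Table 2); later, the original characters would have to be recovered from paper.
2. Match within school and class code, with arm masked. Accept a one-character difference only when the candidate is unique.
3. Reword the sentence in section 9 so that unmatched questionnaires leave only the individually linked analysis. Keep all post-test questionnaires in a supporting comparison of post-test prevalence by arm that accounts for clustering by school and adjusts for school-level baseline prevalence.
4. Report match rates by arm and country and, for baseline questionnaires, by baseline use within arm. The last breakdown is needed because overall rates by arm can look alike while mismatch is selective.

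The cost is a change to the entry mask, a matching program and one extra analysis. The downside is a small risk of false matches, limited by searching only within a class of about 25 to 30 pupils.

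### Teacher presence during the self-report survey has no single rule and is not recorded, so under-reporting of substance use may differ by arm at post-test

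*Protocol*

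**What the plan says.** For the pre-test, Section 8 of the Protocol allows teachers to leave during the survey and adds that, on their presence or absence, "individual agreement will be taken for each class inside the country". For the post-test, Section 11 opens with "Following the same procedures adopted for the pre-test survey" and then says that the teachers "will decide if remain or leave the class". Section 13 carries the same procedures into the possible one-year survey.

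On what is measured, Section 8 states: "The questionnaire will be distributed to the pupils by the center staff and will be self-completed". Section 6 lists "own tobacco, alcohol and substance use" among the questionnaire's main parts.

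On who runs the programme, Section 5 places "the training of teachers in the schools allocated to the intervention groups" after random allocation. Section 10 provides a class-activity form "to be completed by the teacher at the end of each unit, for a total of 12 forms". Under Section 4, control pupils receive only the questionnaire, and control schools are offered training in summer or autumn 2011, after the May 2011 post-test.

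Two safeguards are stated. The project manager and assistants run the survey in both rounds (Sections 8 and 11), and questionnaires are linked by a self-generated anonymous code instead of a personal identifier (Section 11).

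**The concern.** Teachers know their school's arm before either survey round. At post-test they choose whether to be in the room while pupils report behaviour that the programme discourages. In intervention classes the teacher who stays may be the one who taught Unplugged; in control classes no teacher has taught it. This opens two routes to bias:

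- Teachers may stay more often in one arm than in the other.
- Teachers may stay equally often, but pupils may deny use more readily in front of someone who has just taught them the programme.

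Either route can create a difference in reported use where behaviour does not differ. Section 8 plans to take each pupil's baseline status into account, but this does not remove the bias. The second route cannot operate at pre-test, because the programme has not started. The first is not removed either, because presence need not be the same in both rounds. A larger sample does not help, because the bias does not shrink with the number of pupils. If presence is never recorded, no later analysis can examine it.

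**Working it through.** **Step 1: the two rules side by side.**

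| Question | Section 8, pre-test | Section 11, post-test |
|---|---|---|
| Who decides? | An agreement for each class | The teachers |
| Same rule in both arms? | Not stated | Not stated |
| Must presence match the other round? | Not stated | Procedures said to be the same; presence in a class not fixed |
| Is presence recorded? | Not stated | Not stated |

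**Step 2: a model for the size.** The Protocol gives no figure on teacher presence or reporting, so there is nothing of its own to reproduce. All inputs below are assumptions:

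- p = true prevalence, set equal in both arms (no real effect)
- q = share of classes with the teacher present
- s1, s0 = share of true users who report use with and without the teacher present

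Reported prevalence = p × [q × s1 + (1 − q) × s0]. The spurious risk ratio (RR) is the intervention value divided by the control value. Because p cancels, the RR does not depend on prevalence.

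**Step 3: results.**

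| Case | Intervention | Control | RR |
|---|---|---|---|
| Equal presence (50%) and equal reporting, s0 = 0.90, s1 = 0.70 | 0.80 | 0.80 | 1.00 |
| Presence 70% v 30%, s0 = 0.95, s1 = 0.85 | 0.7×0.85 + 0.3×0.95 = 0.88 | 0.3×0.85 + 0.7×0.95 = 0.92 | 0.96 |
| Presence 80% v 20%, same s0 and s1 | 0.87 | 0.93 | 0.94 |
| Presence 70% v 30%, s0 = 0.90, s1 = 0.70 | 0.76 | 0.84 | 0.90 |
| Presence 80% v 20%, same s0 and s1 | 0.74 | 0.86 | 0.86 |
| Presence 50% in both, s0 = 0.90, s1 = 0.70 v 0.85 | 0.5×0.70 + 0.5×0.90 = 0.80 | 0.5×0.85 + 0.5×0.90 = 0.875 | 0.91 |
| Presence 100% in both, s1 = 0.70 v 0.85 | 0.70 | 0.85 | 0.82 |

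A second set assumes full reporting when the teacher is absent (s0 = 1). With the teacher present, 20% or 30% of users deny use in intervention classes and 10% in control classes. At 50% presence this gives 0.90/0.95 = 0.95 and 0.85/0.95 = 0.89. At 100% presence it gives 0.80/0.90 = 0.89 and 0.70/0.90 = 0.78.

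**Step 4: direction.** If teachers stay more often in control classes, the bias reverses. Swapping 70% and 30% gives 0.92/0.88 = 1.05 or 0.84/0.76 = 1.11.

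**Step 5: effect of one rule.** With the teacher out of every class, q = 0 in both arms and the RR returns to s0/s0 = 1.00, provided that reporting without the teacher is the same in both arms. Equal presence alone is not enough, as the last two rows of the table show.

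**The case against.** The strongest reply is that the Protocol already protects reporting. Questionnaires are self-completed under an anonymous code that is piloted beforehand (Section 7), and project staff run the session in both arms. This stands as mitigation. However, the code protects identity; it does not address a pupil's reluctance to answer frankly with the teacher in the room.

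A second reply is that Sections 8 and 11 may describe one arrangement: an agreement made once with each class and carried forward. That reading is possible. The Protocol does not state that presence changes between rounds; it only fails to prevent this. Even on that reading, there is no common rule across arms and no record.

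Three stronger readings are tempting, but the documents do not support them:

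- A reader might take it as stated that the teacher in the room delivered Unplugged. Sections 5 and 10 make this likely, but no section says so, nor that the teacher has a stake in the result.
- A reader might say that every outcome is self-reported substance use. Sections 4 and 6 also list knowledge, opinions, intentions and skills. These too are self-reported, but they are not substance use.
- A reader might conclude that the trial will show a false benefit of a given size. The denial rates above have no source in the documents, and equal presence with equal denial gives 1.00.

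**Conclusion.** The point holds as a flaw in standardising the measurement. The Protocol states who decides on teacher presence in two different ways, sets no rule common to both arms and all rounds, and asks for no record. This permits arm-dependent under-reporting that baseline adjustment would not remove. The size is unknown. Under the assumed rates, a null effect could appear as an RR from 1.00 down to about 0.8 to 0.9. The lower end needs a teacher in every class and clearly stronger denial in intervention classes. A bias in favour of Unplugged is the plausible direction if its deliverer is present, but it is not certain. Even a modest artefact matters here, because the Protocol's own introduction describes the effects of most such programmes as small on tobacco and inconsistent on alcohol and drugs. The change should be made; the point does not show that the trial's result would be wrong.

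**What to change.** Replace the text on teacher presence in Sections 8 and 11 with one rule, and refer to it in Section 13: in both arms and in every round, the class teacher is out of the room while questionnaires are completed and collected by project staff.

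Where a school does not agree, record teacher presence for each class and round, keep those classes in the main analysis, and report a sensitivity analysis by teacher presence. State with it that presence is a post-randomisation feature: dropping or comparing classes on it can itself bias the contrast, so it cannot replace the main analysis. Holding presence constant across rounds is not a substitute, because the concern includes a change in reporting that arises after the programme is taught.

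The cost is small. Project staff are already in the room, so none need be added. Recording is one item per class: at the minimum of 75 schools with three or four classes each, 225 to 300 entries per round (75 × 3 and 75 × 4). The downside is that some schools may object, since the survey is run in agreement with them. The rule also does not remove any reluctance that pupils carry from the programme itself.
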